10.3 Safety

Routine safety and tolerability will be evaluated from the results of reported signs and symptoms, scheduled physical examinations, vital sign measurements, and clinical laboratory test results. More frequent safety evaluations may be performed if clinically indicated or at the discretion of the investigator.

Physical Examination

Complete and symptom-directed physical examinations will be performed by a licensed physician (or physician's assistant or nurse practitioner).

Vital Signs

Vital signs include blood pressure, respiratory rate, pulse rate and temperature.

Safety Laboratory Determinations

Laboratory evaluations will be performed as noted in the Study Calendar.

10.4 Stopping Rules

10.4.1 Toxicity: If 6 of the first 8 treated subjects develop 2 or more CTCAE grade 3 toxicities related to study drug, it will be reviewed by the DSMC to determine if the trial will continue.

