4.4 Study Duration

The estimated duration for the protocol (from start of screening to last subject processed and finishing the study) is 3 to 4 years (Accrual at 2 patients per month. Study duration will be 6 months per patient. Patient will be followed for approximately 2 years after study enrollment).

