15.3 Data and Safety Monitoring Plan

A Data and Safety Monitoring Committee (DSMC) is established at Huntsman Cancer Institute (HCI) and approved by the NCI to assure the well-being of patients enrolled on Investigator-Initiated Trials that do not have an outside monitoring review. Roles and responsibilities of the DSMC are set forth in the NCI-approved plan. The activities of this committee include a quarterly review of adverse events including SAEs, important medical events, significant revisions or amendments to the protocol, and approval of cohort/dose escalations. If the DSMC and/or the PI have concerns about unexpected safety issues, the study will be stopped and will not be resumed until the issues are resolved. The DSMC also reviews and approves audit reports generated by the Research Compliance Office.

All **phase II** studies are reviewed by the full committee at each quarterly DSMC meeting. This includes a review of all serious adverse events (SAEs) occurring in patients treated at HCI or its affiliates as well as all grade 3 or greater toxicities for patients on treatment and within 30-day follow-up window (only if possibly, probably, or definitely related).

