15.4.1 Adverse Events (AE)

An adverse event is the appearance or worsening of any undesirable sign, symptom, or medical condition occurring after starting the study drug, even if the event is not considered to be related to study drug. For the purposes of this study, the terms toxicity and adverse event are used interchangeably. Medical conditions/diseases present before starting study drug are only considered adverse events if they worsen after starting study drug. Abnormal laboratory values or test results constitute adverse events only if they induce clinical signs or symptoms, are considered clinically significant, or require therapy.

The collection of all adverse events will begin after the first dose of study treatment and end 30 days after the last dose of study treatment. The collection of treatment-related adverse events will continue until the last study visit (or until new cancer treatment is initiated, if sooner),

Information about all adverse events, whether volunteered by the subject, discovered by investigator questioning, discovered by clinical research coordinator interview, or detected through physical examination, laboratory test or other means, will be collected and recorded and followed as appropriate.

The occurrence of adverse events should be sought by non-directive questioning of the patient at each visit or phone contact during the study. Adverse events also may be detected when they are volunteered by the patient during or between visits or through physical examination, laboratory test, or other assessments. As far as possible, each adverse event should be evaluated to determine:

1. the severity grade based on CTCAE v.4 (grade 1-5)
2. its relationship to Radium-223 or EBRT (definite, probable, possible, unlikely, not related).
3. its duration (start and end dates or if continuing at final exam)
4. action taken (no action taken; study drug dosage adjusted/temporarily interrupted; study drug permanently discontinued due to this adverse event; concomitant medication taken; non-drug therapy given; hospitalization/prolonged hospitalization)
5. whether it constitutes an SAE

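### The numerical toxicity trigger in 10.4.1 counts a narrower set of events than the DSMC reviews, and its trigger probabilities are not stated

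*Combined protocol and SAP*

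**What the plan says.** Section 10.4.1 sets one toxicity rule. The condition is "If 6 of the first 8 treated subjects develop 2 or more CTCAE grade 3 toxicities related to study drug", and the consequence is that "it will be reviewed by the DSMC to determine if the trial will continue". No unacceptable rate, counting period or trigger probability is given there or in section 11.

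Other sections describe the safety data more broadly:

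- **Section 15.4.1** has each event assessed for "the severity grade based on CTCAE v.4 (grade 1-5") and for "its relationship to Radium-223 or EBRT (definite, probable, possible, unlikely, not related"). Grades 4 and 5 are therefore separate categories from grade 3, and the two treatments are both named in attribution.
- **Section 15.3** says of phase II trials that such "studies are reviewed by the full committee at each quarterly DSMC meeting". That review takes in all SAEs and "all grade 3 or greater toxicities for patients on treatment and within 30-day follow-up window", where at least possibly related. The section also provides for a halt if the committee or the principal investigator is concerned about safety problems that were not expected.
- **Sections 15.4.2 and 15.5** require SAEs to be reported whether or not thought related, on a form due within 1 business day, with the DSMC among the recipients.

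**The concern.** The treatment under test is Radium-223 combined with ablative radiotherapy to every oligometastatic site, and secondary objective 1.2.6 covers adverse events of both. The numerical trigger names one grade and, on its wording, one of the two components. Where the protocol means to include higher grades it says so elsewhere: grade 3 or 4 in the myelosuppression rules of section 8.1.1, grade 3+ in the background data of section 3.1.4, and grade 3 or greater in section 15.3. In section 8.1.1 the term study drug is used for the injected agent.

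If 10.4.1 is followed as written, a worse event can fail to count where a milder one would, and radiotherapy toxicity falls outside the count. If something broader was meant, those applying the rule have to guess. Either way, the DSMC could disagree about whether the trigger has been met. Without trigger probabilities, neither the DSMC nor the IRB can see what level of toxicity the rule is built to detect.

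**Working it through.** **Step 1. Apply the literal wording to individual men.** Aligned here means grade 3 or greater (15.3), related to Radium-223 or EBRT (15.4.1).

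| A man's related events | Counts under 10.4.1 as written | Counts if aligned |
|---|---|---|
| Two grade 3, Radium-223 | Yes | Yes |
| One grade 3 and one grade 4, Radium-223 | No | Yes |
| Two grade 4, Radium-223 | No | Yes |
| One grade 3 Radium-223 and one grade 3 EBRT only | No | Yes |
| Two grade 3, EBRT only | No | Yes |
| A single grade 5 event | No | No |

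Rows two to five are the gap. The last row arises from the two-event requirement, not from the grade wording, so aligning the text does not change it.

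**Step 2. Trigger probability.** The plan states no figure for this rule, so there is none to reproduce. (The 93% power in section 11 for the primary test does reproduce: P(X ≥ 2) with n = 20 and p = 0.20 is 0.931. It is unaffected by this point.)

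Inputs from 10.4.1: 8 men, and a trigger at 6, read as 6 or more. Let p be the true share of men with two or more qualifying events. The documents do not give p, so a range is assumed, with men independent and p the same for each.

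P(trigger) = 28p⁶(1−p)² + 8p⁷(1−p) + p⁸

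- At p = 0.5: (28 + 8 + 1)/256 = 37/256 = 0.145.
- At p = 0.3: 0.01000 + 0.00122 + 0.00007 = 0.011.

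| Assumed p | P(at least 6 of 8) |
|---|---|
| 30% | 1.1% |
| 40% | 5.0% |
| 50% | 14.5% |
| 60% | 31.5% |
| 70% | 55.2% |
| 80% | 79.7% |

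An even chance of triggering needs p of about 68%. An 80% chance needs p of about 80%.

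**Step 3. What aligning the wording could do.** It can only raise p, by an amount the documents do not allow anyone to estimate. For illustration, a rise from 30% to 40% moves the trigger chance from 1.1% to 5.0%, and a rise from 40% to 50% moves it from 5.0% to 14.5%.

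**The case against.** The strongest reply is that 10.4.1 is not what protects these men. Its only consequence is a DSMC review, and section 15.3 already supplies one every quarter on a broader set of events. Fatal and life-threatening events are SAEs and are reported promptly whatever their attribution. Section 8.1.1 adds patient-level rules for grade 3 or 4 cytopenias. Grade 3 may also simply be loose wording for grade 3 or higher.

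Most of this stands. A reader might infer that the trial could overlook its worst events, or that 10.4.1 is its only safety safeguard; the documents support neither. What remains is that the quarterly route has no preset count. Its stop clause is limited to unexpected issues, whereas section 3.1.4 describes myelosuppression as already known with Radium-223. And if the wording is merely loose, correcting it is easier still.

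A reader might also infer that the rule acts too late to matter. Section 4.4 gives "Accrual at 2 patients per month" and "Study duration will be 6 months per patient". With one man every half month, the eighth enters at month 3.5 and finishes at month 9.5, when the twentieth enters. But 10.4.1 does not wait for the eighth man to finish: it is met as soon as a sixth man qualifies. A simulation at that accrual, with events spread over each man's 6 months of treatment (an assumption), put every trigger before the last enrolment, typically with 14 to 16 men enrolled. No timing defect is established.

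Finally, a low trigger chance at a tolerable rate is what a safety rule should show. A figure of 1.1% at 30% is a fault only if 30% is unacceptable, and the documents do not say whether it is.

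**Conclusion.** The point holds as a mismatch of wording together with a missing statement of operating characteristics. Sections 10.4.1, 15.3 and 15.4.1 do not agree on which grades and which attributions matter. On the literal text, the one numerical trial-level trigger leaves out grade 4 and 5 events and EBRT-only events. This rests on the wording alone and needs no assumption about rates.

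The trigger chance runs from 1.1% at an assumed rate of 30% to 79.7% at 80%. Those figures assume independent men with a common rate and describe how the rule behaves. Because no unacceptable rate is stated, they do not show that 6 of 8 is the wrong threshold or that the rule seldom triggers when it should.

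The practical consequence is moderate. Severe events reach the DSMC by other routes, and the primary analysis and sample size are untouched. The correction is still worth making, because a preset count is useful only if everyone counts the same events.

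**What to change.** Reconcile 10.4.1 with 15.3 and 15.4.1, so that the count uses grade 3 or greater and events related to Radium-223 or EBRT. Add the trigger probabilities from the second table above to 10.4.1 or section 11, labelled as calculated at assumed rates.

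The numerical threshold, and whether to continue counting beyond the first 8 men, should be left to the sponsor and the DSMC. Extension is not a small change. If it meant 6 men in total among all 20, the trigger chance at a true rate of 30% would rise from 1.1% to about 58% (P(X ≥ 6), n = 20, p = 0.30). At 20% it would rise from 0.1% to about 20%.

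The cost is a few lines in an amendment and a tally from data the DSMC already receives, using the attribution recorded under 15.4.1. The downside is a somewhat higher chance of a DSMC review.

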11 STATISTICAL CONSIDERATIONS

The primary objective is to determine the hormone-therapy-free survival time for men treated with concurrent EBRT and Radium-223 and determine whether 20% of subjects do not meet the progression endpoint and require ADT at 15 months. The primary outcome is 15 months hormone- (or other systemic) therapy-free survival. The null hypothesis is that 99% of subjects will start systemic therapy within 15 months. The alternative hypothesis is that 80% of subjects will start systemic therapy within 15 months. With 20 evaluable subjects there will be 93% power for this alternative hypothesis using an exact binomial test at the one-sided 0.05 significance level. The null hypothesis will be rejected if 2 or more out of 20 subjects are not placed on systemic therapy within one year.

One of the secondary endpoints is to determine the hormone-therapy-free survival time for men treated with concurrent EBRT and Radium-223 and determine whether it is a 30% risk reduction over the SWOG intermittent ADT historic cohort. This secondary hypothesis will be tested only if the primary null hypothesis is rejected. The outcome for

this secondary hypothesis is 15 month hormone- (or other systemic) therapy-free survival. In 2012 a SWOG cooperative group trial reported that 78% of subjects on intermittent androgen therapy had resumed ADT within 15 months, and this proportion will be used as a null hypothesis. With 20 evaluable subjects, and a null hypothesis that 78% or more of patients will start systemic therapy within 15 months there will be 80% power to detect an alternative hypothesis that 48% or fewer will start systemic therapy within 15 month using an exact binomial test at one-sided alpha =0.05 significance level.

Additional, secondary endpoints are time to first skeletal related event (SRE), overall survival, PSA doubling time, overall survival and toxicities. All secondary endpoints will be evaluated descriptively. Time to first SRE, OS, and PSA doubling time will be analyzed via Kaplan-Meier product limit methods and associated 95% confidence intervals. Toxicities will be tabulated using CTAE version 4.0. The number and proportion of subjects with toxicities will be reported.

Exploratory endpoints are to evaluate if a commercially available cell-cycle progression gene assay (Myriad CCP) performed on the original prostate biopsy or surgical pathology specimen correlates with biochemical or clinical progression free survival in the study population.

Correlations with survival endpoints will be performed using exploratory Cox proportional hazards regression analysis.

Primary analysis and report planned at 15 months of follow up for all enrollees.

Health-related Quality of Life as scored by EPIC urinary, bowel, sexual, and hormonal domains, as well as PROMIS-29 questionnaires.

Medians, ranges, and quartiles will be computed for all health-related Quality of Life domains. Exploratory logrank tests will be used to relate domain scores to survival outcomes (hormone-free survival, time to first skeletal event, overall survival, and PSA doubling time).

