Study Duration	3-4 years (accrual at 2 patients per month. Study duration 6 months per patient. 2 year follow up.)
Study Center(s)	This is a single site study conducted at the Huntsman Cancer Institute
Objectives	Primary Objective: Freedom from Androgen Deprivation Therapy (ADT) or other antineoplastic systemic at 15 months. Secondary Objective: QOL assessments, Progression Free Survival, Overall Survival
Number of Subjects	20
Diagnosis and Main Eligibility Criteria	Men with Prostate Cancer and no more than 5 sites of bony metastatic disease without visceral involvement.
Study Product, Dose, Route, Regimen	
 Radium-223 55 kBq (1.49 mCi)/kg (+/- 10% total dose) at study enrollment, and then every 4 weeks following definitive radiation therapy for a total of six Radium-223 infusions. Hypofractionated Radiotherapy to all oligometastatic sites
Duration of administration	6 months of therapy
Reference therapy	Institutional Care Standard (99% of subjects starting Androgen Deprivation Therapy by 15 months)

Statistical Methodology	Assess the proportion of ADT naïve men who progress and require ADT at 15 months.
-------------------------	-----------------------------------------------------------------------------------

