1.1 Primary Objectives and Endpoint

1.1.1 Determine if 20% of ADT naïve men treated with concurrent EBRT and Radium-223 will not require ADT for progression by 15 months.
Endpoint: Determine the time from start of study therapy to start of ADT.

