10.1 Primary Endpoint – 15 month Hormone Free Survival

The primary objective is to determine the hormone-therapy-free survival time for men treated with sequential EBRT and Radium-223 and determine whether it is a 20% risk reduction over the institutional comparator of 100% use of systemic therapy by 15 months. The primary outcome is 15 months hormone-free survival. Patients will remain on study treatment for the duration defined by the calendar or for disease progression. Patients will be followed up to determine the start of ADT which will be used to measure the primary end point.

For the purposes of this study, progression will be measured after the completion of EBRT and the delivery of Cycle 2 of Radium-223 and defined as either:

Biochemical Progression:

- For those subjects whose PSA is greater than 20ng/ml at baseline who do not have any PSA decrease after starting therapy: biochemical progression will be defined as a 10% rise over the baseline.

- For those subjects whose PSA is greater than 20ng/ml at baseline, who demonstrate decrease in PSA after study treatment: if the PSA nadir remains > 20ng/ml, biochemical progression will be defined as a PSA rise greater than 10% of the PSA nadir. If the PSA nadir is < 20ng/ml, biochemical progression will be defined as a PSA rise greater than 10% of the PSA nadir.

-For those subjects whose PSA is less than 20ng/ml at baseline: biochemical progression will be defined as PSA >20ng/ml and 10%.

*Any PSA test that would meet a failure definition has to be validated through Huntsman Cancer Institute or a Veterans Affairs Hospital with a repeat PSA test no sooner than 5 days and no later than 14 days from the initial notification of the result demonstrating progression.

OR

Radiographic progression: Any new, progressing, or reappearing lesion on Bone Scan, CT/Scan, or MRI compared to the same scan performed previously. Radiographic Progression will be determined by Prostate Cancer Clinical Trials Working Group (PCWG2) and RECIST 1.1 as described below (section 10.1.1).

* Of note: For a patient to meet radiographic progression criterion for appearance of new bone lesion only, the patient must demonstrate appearance of new bone disease, as confirmed by the treating radiation oncologist, and also meet the biochemical progression definition set out above.

OR

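### The rejection rule for the primary test is stated at one year, but the endpoint, hypotheses, power and analysis timing are all at 15 months

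*Combined protocol and SAP*

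**What the plan says.** The first paragraph of Section 11 (Statistical Considerations) sets out the primary test. The outcome is freedom from hormone or other systemic therapy at 15 months. On the null, "The null hypothesis is that 99% of subjects will start systemic therapy within 15 months". On the alternative, "The alternative hypothesis is that 80% of subjects will start systemic therapy within 15 months". The test is an exact binomial test in 20 evaluable subjects at one-sided 0.05, with 93% power stated. The paragraph then closes with the decision rule: "The null hypothesis will be rejected if 2 or more out of 20 subjects are not placed on systemic therapy within one year".

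The other places that give a time point for this endpoint use 15 months:

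- Section 1.1 (primary objective): the target is the share of men who "will not require ADT for progression by 15 months".
- Section 10.1: "The primary outcome is 15 months hormone-free survival".
- Study Summary, reference therapy: "99% of subjects starting Androgen Deprivation Therapy by 15 months".
- Section 2, Comparator Cohort: the institutional experience and the goal of the study are both given at 15 months.
- Section 11, timing: "Primary analysis and report planned at 15 months of follow up for all enrollees".

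The secondary test against the SWOG intermittent cohort is also at 15 months, with "80% power to detect an alternative hypothesis that 48% or fewer will start systemic therapy within 15 month". No section gives a 12-month rate, a reason for a 12-month decision point, or a correction of the rule.

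**The concern.** The sentence at fault decides the primary verdict, and it is the only place where the cut-off is written down. Followed word for word, it classifies men by their status at 12 months, while the hypotheses being tested concern their status at 15 months.

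The difference runs one way. Every man free of systemic therapy at 15 months was also free at 12 months, so the one-year count can equal or exceed the 15-month count but never fall below it. With a cut-off of two men, one late start can decide the result. If two men are free at month 12 and one of them starts ADT in month 14, the rule as written rejects the null and the rule at 15 months does not.

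This is an open-label, single-arm trial. If the wording stays, either reading could be defended after the data are known, and the literal one favours a positive result.

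**Working it through.** **Inputs, all from Section 11.** n = 20; free of systemic therapy at 15 months: 1 − 0.99 = 0.01 under the null and 1 − 0.80 = 0.20 under the alternative; one-sided alpha 0.05; stated power 93%. Let X15 and X12 be the numbers free of therapy at 15 and 12 months.

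**Step 1: reproduce the plan's figure at 15 months.** P(X ≥ 2 | p) = 1 − (1−p)^20 − 20p(1−p)^19.

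- Null: 1 − 0.8179 − 0.1652 = 0.0169.
- Alternative: 1 − 0.0115 − 0.0576 = 0.9308, the stated 93%.

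| Cut-off | Type I error (p = 0.01) | Power (p = 0.20) |
|---|---|---|
| ≥ 1 | 18.2% | 98.8% |
| ≥ 2 | 1.69% | 93.1% |
| ≥ 3 | 0.10% | 79.4% |

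Two is the smallest cut-off that keeps type I error within 5%, and it gives the stated power. The rule was evidently derived from the 15-month rates.

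**Step 2: the rule as written, without assuming a 12-month rate.** Since X12 ≥ X15, type I error at one year is at least 1.69%. Solving P(X ≥ 2 | p) = 0.05 for n = 20 gives p = 0.0181. Control at 5% is therefore lost once more than about 1.8% of patients under the null are still free of therapy at 12 months, compared with 1% at 15 months.

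**Step 3: illustration only.** The documents give no 12-month rate or hazard shape. Assume a Weibull curve through the plan's 15-month rates, S(12) = S(15)^((12/15)^k), where k = 1 is a constant hazard. For example, under the null with k = 1, S(12) = 0.01^0.8 = 0.0251. Because X15 ≥ 2 implies X12 ≥ 2, the chance that the two readings give opposite verdicts is P(X12 ≥ 2) − P(X15 ≥ 2).

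| Scenario | k | S(12) | P(reject) at one year | Opposite verdicts |
|---|---|---|---|---|
| Null, S(15) = 0.01 | 0.5 | 1.63% | 4.1% | 2.5% |
| | 1 | 2.51% | 8.9% | 7.2% |
| | 1.5 | 3.71% | 16.8% | 15.2% |
| Alternative, S(15) = 0.20 | 0.5 | 23.7% | 96.8% | 3.7% |
| | 1 | 27.6% | 98.6% | 5.6% |
| | 1.5 | 31.6% | 99.5% | 6.4% |

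**Step 4: does the secondary SWOG test change?** It is run only if the primary null is rejected. Its null is 1 − 0.78 = 0.22 free and its alternative 1 − 0.48 = 0.52 free. P(X ≥ 8 | 0.22) = 5.36%, above 5%; P(X ≥ 9 | 0.22) = 1.86%; P(X ≥ 9 | 0.52) = 80.2%, the stated 80%. It therefore rejects only with 9 or more free at 15 months, and the primary null is then rejected under either reading. Its result cannot change.

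**The case against.** The best reply is that the plan almost corrects itself. If the rejection sentence were deleted, the remaining specification (exact binomial, 20 subjects, one-sided 0.05, 15-month rates of 99% and 80%) would still lead to 2 of 20 at 15 months, and the stated power confirms it. To apply the one-year reading, an analyst would have to count men known to have started therapy as successes on an endpoint named for its 15-month time point. Start of ADT is recorded as a time from start of study therapy, so 15-month status can be computed whichever wording stands, and no data are lost if the slip is noticed late.

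The illustrative percentages can also be challenged. They rest on an assumed curve and a chosen range of shapes. A shape of 0.25 gives a type I error of 2.7% and a shape of 3 gives 57.7%; at a shape of 0.6 it is 4.9%, still within 5%.

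Much of this stands. The intent is clear, the literal reading is unlikely to be adopted in good faith, and the Weibull figures are not estimates of this trial's error rate. But the point does not depend on them. The contradiction lies in current text, it sits in the primary decision rule, and it errs towards rejection. That the intended time point can be inferred makes the correction safe; it does not make it unnecessary.

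**Conclusion.** The concern holds. The primary rejection rule is wrong as written: its time point contradicts the endpoint and every rate from which its cut-off was derived. What follows without assumption is that the cut-off has 1.69% type I error and 93.1% power at 15 months, that the one-year reading can only raise the chance of rejection, and that 5% is passed at a 12-month null rate of about 1.8%. The size of any inflation is unknown, because the plan gives no 12-month rate; 8.9% under a constant hazard is an illustration, and some hazard shapes produce no breach of 5%.

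The harm is confined to the primary verdict. Power is not reduced, and the secondary SWOG result is unaffected. It must still be corrected, because it is the decision rule for the primary endpoint and two readings should not be available once results are known.

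**What to change.** In the last sentence of the first paragraph of Section 11, replace *within one year* with *within 15 months*, and make the change before the primary analysis. The null is then rejected if at least 2 of the 20 subjects have not been placed on systemic therapy by 15 months. Change nothing else: the 20 subjects, the cut-off of 2, the alpha and the stated power are already right for 15 months.

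The cost is one phrase in an amendment, with no effect on sample size, analysis population, visits or data. The corrected rule is slightly harder to meet than the literal one: at the 20% alternative with a constant hazard, the chance of rejection is 93.1% instead of 98.6%. That is the power the plan already states.

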1 OBJECTIVES

We hypothesize that treatment with Radium-223 and focal radiotherapy to 5 or fewer sites of clinically detectable bony metastases will delay the time to start systemic therapies (androgen deprivation therapies (ADT) or other antineoplastic systemic therapies). This hypothesis will be tested through the following aims.

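### Section 11's primary decision rule counts subjects at one year, although its hypotheses, power and planned analysis are all at 15 months

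*Combined protocol and SAP*

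**What the plan says.** The primary outcome in Section 11 is 15-month survival free of hormone or other systemic therapy. The null reads "The null hypothesis is that 99% of subjects will start systemic therapy within 15 months", the alternative is 80% starting by the same time, and 20 evaluable subjects are said to give 93% power with an exact binomial test at one-sided 0.05. The cutoff follows: "The null hypothesis will be rejected if 2 or more out of 20 subjects are not placed on systemic therapy within one year". Section 11 later adds "Primary analysis and report planned at 15 months of follow up for all enrollees". The Study Summary and Sections 1.1.1, 2 (Comparator Cohort) and 10.1 also use 15 months.

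Two related statements bear on interpretation.

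- **The 20% figure.** Section 1.1.1 asks whether 20% of men "will not require ADT for progression by 15 months", and Section 11 opens with the aim to "determine whether 20% of subjects do not meet the progression endpoint and require ADT at 15 months". In the test itself, 20% free is the alternative used for power. Section 11 names intervals for other endpoints ("Time to first SRE, OS, and PSA doubling time will be analyzed via Kaplan-Meier product limit methods and associated 95% confidence intervals") but none for the primary proportion.
- **The SWOG comparison.** Sections 1.2.1 and 11 call the target a 30% risk reduction. Section 11 powers it as 78% against 48% starting therapy: "there will be 80% power to detect an alternative hypothesis that 48% or fewer will start systemic therapy within 15 month". It is tested only if the primary null is rejected.

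**The concern.** The sentence with the wrong time point is the only one that states the cutoff, so it is the rule an analyst would follow. A man who starts ADT in month 13 or 14 is free of therapy under the printed rule and a failure under the endpoint. Since two subjects decide the trial, one such man can change the result. The stated error rate and power were worked out for a 15-month count and do not carry over to a 12-month count.

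The two clarifications matter less. Because the objective is worded as determining whether 20% stay free, a rejection at 2 of 20 (10% observed) could be reported as having reached 20%. A 30% risk reduction without a scale could be read as relative, which is not the target that was powered.

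**Working it through.** **Inputs (Section 11).** n = 20; free rate 0.01 under the null and 0.20 under the alternative, both at 15 months; reject if X ≥ 2 are free; one-sided 0.05. With X binomial(20, p),

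P(X ≥ 2) = 1 − (1 − p)^20 − 20p(1 − p)^19.

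**The plan's own figures, at 15 months.**

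- Type I error, p = 0.01: 1 − 0.8179 − 0.1652 = 0.0169.
- Power, p = 0.20: 1 − 0.0115 − 0.0576 = 0.9308, which reproduces 93%.
- A cutoff of 1 would give type I error 1 − 0.8179 = 0.1821, so 2 is the right cutoff for one-sided 0.05.

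**The same rule applied at 12 months.** The documents do not give the free rate at 12 months that goes with 1% at 15 months, so the shape of the time-to-start curve has to be assumed. For a Weibull curve with shape k, S(12) = S(15)^((12/15)^k).

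| Assumed shape k | Exponent 0.8^k | Free at 12 months if 1% free at 15 | P(X ≥ 2) |
|---|---|---|---|
| 0.5 (starts bunched early) | 0.894 | 1.63% | 4.1% |
| 1 (constant hazard) | 0.800 | 2.51% | 8.9% |
| 2 (starts bunched late) | 0.640 | 5.25% | 28.3% |

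P(X ≥ 2) reaches 5% at p = 1.81%, so any 12-month free rate above about 1.8% takes the rule past its stated level. Under constant hazard, 2.5% − 1.0% = 1.5% of subjects would start between months 12 and 15 and be counted as successes. Nominal power would rise too: 0.20^0.8 = 0.276, giving P(X ≥ 2) = 98.6%, but that is no longer power for the stated alternative.

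**Precision of the primary proportion (exact Clopper-Pearson 95% intervals).**

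| Free of 20 | Observed | 95% interval |
|---|---|---|
| 1 | 5% | 0.1% to 24.9% |
| 2 | 10% | 1.2% to 31.7% |
| 3 | 15% | 3.2% to 37.9% |
| 8 | 40% | 19.1% to 64.0% |
| 9 | 45% | 23.1% to 68.5% |

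The interval contains 20% for every count from 1 to 8.

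**SWOG comparison.** The free rates are 0.22 and 0.52. P(X ≥ 8 | 0.22) = 0.0536 and P(X ≥ 9 | 0.22) = 0.0186, so the implied cutoff is 9 of 20. P(X ≥ 9 | 0.52) = 0.8023, which reproduces 80%. The difference is 78 − 48 = 30 percentage points, or 30/78 = 38.5% relative. A 30% relative reduction would be 0.78 × 0.70 = 54.6% starting.

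**The case against.** The best defence is that one year is a stray phrase. Everything around it says 15 months, the analysis is scheduled at 15 months, and a sensible analyst would read it so. The intention is indeed clear, and the error figures above arise only if the sentence is applied literally and under an assumed curve. At shape 0.5 the error is still below 5%. That limits the size of the problem but does not remove the contradiction in the rule that decides the trial.

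A reader might also infer three stronger faults, which the documents do not support.

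- **That a cutoff at 10% is wrong because the objective is 20%.** A single-arm cutoff normally lies between the null and alternative rates. Section 11 names both rates, Section 10.1 frames the aim against institutional use of systemic therapy, and no test of a rate above 20% is planned. Nor does any section say that rejection will be reported as establishing 20%. The missing interval would not show that 20% was missed: at 2 of 20 it includes 20%.
- **That success could be spurious because ADT is merely deferred.** Section 1 hypothesises that treatment delays systemic therapy and says "This hypothesis will be tested through the following aims". Section 2 describes immediate ADT as the standard of care, and Section 7.3 bars ADT alongside study treatment. One arm cannot separate treatment effect from deferral. The single-arm design is openly declared, however, and no deferral-only rate is given, so the size cannot be stated. This is a limit to note when results are interpreted.
- **That the SWOG power is wrong.** The 78% and 48% stand in the same paragraph as the power, so the tested target is unambiguous and the 80% is right. Only the label lacks a scale.

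**Conclusion.** The primary decision rule is wrong as printed and should be corrected. The design beneath it is sound: the sample size, cutoff and both powers reproduce. If the rule were applied at one year, the type I error would no longer follow from the stated null. Whether it passes 5% depends on when men start therapy, which the documents do not report. Early starts, as under immediate ADT, point to the lower end of the range; starts deferred until progression on study point to the upper end. That the two time points conflict needs no assumption.

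The 20% wording, the missing interval and the SWOG label are matters of clarity. They affect what may be claimed from a rejection and do not change the test.

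**What to change.** In the Section 11 decision rule, replace one year with 15 months, before the primary result is known. Keep the 20 subjects, the cutoff of 2, the tests and the gating.

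Two clarifications can go in the same amendment:

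1. In Sections 1.1.1, 10.1 and 11, say that the test is of a 15-month free rate above 1%, with 20% as the powered alternative. Say also that the proportion will be reported with its exact 95% confidence interval, and that rejection alone will not be reported as establishing 20%. The interval is there to show precision.
2. In Sections 1.2.1 and 11, label the SWOG target as 30 percentage points (78% to 48% starting therapy; 38.5% relative).

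The cost is one wording amendment through the IRB. It adds no patients, assessments or delay, since the analysis is already planned at 15 months. The downside is a slightly less favourable permitted claim: a man who starts therapy between months 12 and 15 is not a success, and 2 or 3 of 20 free may be reported only as exceeding 1%.
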